7.5 Secondary Objective Pharmacokinetic Analysis

To describe the pharmacokinetics of SYN023 in enrollees using non compartmental analysis, Vd, C_{max}, T_{max}, AUC_{0-t}, AUC_{0-inf}, t_{1/2}, Cl, and λ_z will be calculated when possible in the per-protocol and as treated populations. Individual analyses will be performed and descriptive statistics will be used to describe the results of individual analyses. PK parameters for SYN023 Mab will be estimated using non-compartmental analysis. Vd, C_{max}, T_{max}, AUC_{0-t}, AUC_{0-inf}, t_{1/2}, Cl, and λ_z will be calculated when possible in the per-protocol and as treated populations.

7.7 Secondary Objective Safety Analyses

Safety analyses will be performed using the safety population as defined in Section 7.1. Summaries will be presented by risk group and treatment group for all subjects in the safety population. The safety profile of Study Drug will be described by treatment group. The primary variable for evaluation of the safety profile will be the number and percentage of adverse events

recorded at all available post- Study Drug administration time points. For all presentations of adverse events, additional summaries based on reporting period of adverse events following each Study Drug administration may also be presented.

The number (percentage) of subjects with adverse events will be summarized by MedDRA system organ class (SOC) and preferred term (PT). Additional summaries will present the number (percentage) of subjects with adverse events by severity and by relationship to Study Drug; each subject will be counted once per PT at the greatest severity or most related state recorded for that term.

Separate summaries of the number (percentage) of subjects with adverse events will also be presented. Adverse events will also be summarized by severity and relationship to Study Drug. Each subject will be counted once per preferred term at the greatest severity or most related state recorded for that term.

Serious adverse events will be recorded through the final study visit for all subjects. Listings will be provided for subjects with serious adverse events.

Listings will be provided for subjects who have discontinued prematurely due to an adverse event.

The number (percentage) of subjects with post- Study Drug administration clinical laboratory values or vital sign values recorded as newly abnormal or increased by a toxicity grade following Study Drug administration and meeting toxicity mild criteria (Grade 1) or above as specified in the Toxicity Table will be tabulated at each post- Study Drug administration time point and overall. Clinical laboratory and vital sign abnormalities will also be reported as adverse events and will be included in the summary of adverse events.

The sample size of 190 subjects per treatment group will also permit an initial estimate of general safety and tolerability. An approximation to the upper 95% confidence bound on the true rate of occurrence for a Study Drug-associated adverse event not encountered in 190 subjects is 1.6%.

7.7.1 Adverse Events

The safety profile of the Study Drugs will be described by treatment group. The primary variable for evaluation of the safety profile will be the number and percentage of unsolicited and solicited adverse events recorded at all available post-vaccination time points. For all presentations of adverse events, additional summaries based on reporting period of adverse events following each Study Drug may also be presented.

The number (percentage) of subjects with adverse events will be summarized by MedDRA system organ class (SOC) and preferred term (PT). Additional summaries will present the

number (percentage) of subjects with adverse events by severity and by relationship to Study Drug; each subject will be counted once per PT at the greatest severity or most related state recorded for that term.

Separate summaries of the number (percentage) of subjects with solicited adverse events will also be presented. Solicited adverse events will also be summarized by severity and relationship to Study Drug; each subject will be counted once per PT at the greatest severity or most related state recorded for that term.

In addition, dose-safety curves may be produced to examine the proportion of subjects who experience adverse events by treatment regimen.

Serious adverse events will be recorded through the final study visit for all subjects. Listings will be provided for subjects with serious adverse events.

Listings will be provided for subjects who have discontinued prematurely due to an adverse event.

The number (percentage) of subjects with post-vaccination clinical laboratory values or vital sign values recorded as newly abnormal following study vaccination and meeting toxicity mild criteria (Grade 1) or above as specified in the Toxicity Table (Appendix B) will be tabulated at each post-vaccination time point and overall. Clinical laboratory and vital sign abnormalities will also be reported as adverse events and will be included in the summary of adverse events.

7.7.2 Clinical Laboratory and Vital Sign Parameters

For each clinical laboratory parameter and vital sign parameter pre-specified in the protocol, summary statistics for continuous parameters will be presented by treatment regimen for all pre- and post-vaccination assessments and for change from pre-vaccination to post-vaccination assessments.

7.8 Sample Size Considerations Primary Objective: Composite Endpoint Element

Since the primary objective is composite multiple endpoints will be determined. Each endpoint will have different requirements on the Study sample size determination. The contribution of various endpoints to sample size is tabulated in Table 7.8-1. The specific analyses are discussed in Sections 7.81 - .

Table 7.8-1 Sample Size Estimates for Pharmacodynamic Endpoints (all 80% power, alpha ≤0.025)

CONFIDENTIAL

RVNA GMC	Priority	Sample Size total 1:1	Mean ratio SYN/HRIG	Margin	CI	CV %
Superiority Study Day 8	Primary	<10	>10.0	10%	95	16.11
Non inferiority Study Day 99 GMC	Primary	138	0.88	20%	95	17.00
Non inferiority Study Day 99 percent subjects ≥ 0.5 IU/mL	Primary	72	1.0	10%	95	NA
Superiority Study Day 3	Secondary	<10	>10.0	10%	95	9.83
Superiority AUEC ₁₋₁₅	Secondary	320	1.45	10%	90	108.78

7.8.1 Superiority of Geometric Mean of RVNA Study Day 8

Superiority test for the ratio of two geometric means is used for determining the sample size. The null hypothesis is that the ratio for the two treatments is less than the defined margin that is expressed as:

$$H_0: \emptyset \leq \emptyset_L \text{ where } \emptyset_L > 1$$

Where, $\emptyset = \frac{GM_{SYN023}}{GM_{HRIG}}$; GM is the geometric mean.

The alternative hypothesis for superiority is expressed as: $H_1: \emptyset > \emptyset_L$. The ratio of superiority is more than ten-fold. The sample size required for this comparison is less than 10.

7.8.2 Non-inferiority of Geometric Serum RVNA on Study Day 99

The timepoint selected for non-inferiority in the current trial is based on need for a “later” timepoint at which to evaluate vaccine immunogenicity is from historical data from protocol SYN023-002 for which there are Study Day 84 and Study Day 112 timepoint (Table 7.8.2-1). The Study Day 99 is selected as being between these timepoints and closest for estimation.

The 20% margin was selected since it is a recommended bioequivalence margin for a lower bound of 0.8 (FDA 2001). Applying this margin to historical data near the Study Day 99 timepoint shows RVNA concentrations both well above the 0.5 IU/mL and should provide protective concentration in all subjects (Table 7.8.2-1).

Table 7.8.2-1 RVNA Historical Values by Timepoint for SYN023-002 Protocol

Visit	SYN023			HRIG		
	N	Geometric Mean	95% CI	N	Geometric Mean	95% CI
Day 42	73	8.05	(6.58, 9.85)	76	9.18	(7.91, 10.66)
Day 84	72	2.33	(1.79, 3.03)	75	2.75	(2.27, 3.33)
Day 112	73	1.43	(1.09, 1.87)	76	1.71	(1.38, 2.11)

Non-Inferiority test for ratio of two geometric means is used for determining the sample size. The null hypothesis is that the ratio for the two treatments is less than the defined margin which is expressed as:

$$H_0: \emptyset \leq \emptyset_L \text{ where } \emptyset_L < 1$$

The alternative hypothesis for superiority is $H_1: \emptyset > \emptyset_L$. The calculated ratio between SYN023/RIG and the 95% confidence intervals for the ratio are presented in Table 7.8.2-2 and were used as inputs for the sample size calculation in PASS 15 software.

Table 7.8.2-2: Ratio (SYN023/HRIG) and 95% Geometric Confidence Intervals for Each Time-point for RVNA from SYN023-002 Protocol, Historical Data

Time Point	Ratio (SYN023/HRIG) for RVNA- SYN023-002	95% Geometric Means Ratio CI		CV
Day 35	81.28%	62.19%	106.23%	13.59%
Day 42	88.94%	68.79%	114.99%	13.04%
Day 84	88.50%	64.04%	122.30%	16.47%
Day 112	86.94%	61.88%	122.15%	17.32%

The sample size is calculated at 80% power with 20% margin of non-inferiority and equal allowance (number of subjects in group 1 = number of subjects in group 2) and alpha is taken to be 0.025.

The non-inferiority of serum GMC RVNA on study day 84 in SYN023 recipients (above) with respect to HRIG recipients would require the sample size of 138 for 80% power with an expected true geometric means ratio 88.00%. Note that based on historic data from protocol SYN023-002 the geometric ratio from Study Day 42 through Study Day 112 is stable and therefore it is expected that a true ratio of 88.00% is reasonable to determine non-inferiority at Study Day 99.

7.8.3 Non-inferiority of Percentage of Subjects with Serum RVNA ≥ 0.5 IU/mL on Study Day 99

20 % margin of noninferiority was selected since it is a recommended bioequivalence margin for a lower bound of 0.8 (FDA 2001). Historical SYN023 data is presented In Table 7.8.3-1.

Table 7.8.3-1 Historical Percentage of Subjects with RVNA ≥ 0.5 IU/mL

DAY	SYN023 + Vaccine		RIG + Vaccine	
	≥ 0.5 IU/mL Count (percentage)	Total	≥ 0.5 IU/mL Count (percentage)	Total
0	3 (4.0%)	75	1 (1.3%)	76
1	67 (90.5%)	74	1 (1.3%)	75
3	74 (98.7%)	75	1 (1.3%)	76
7	75 (100.0%)	75	6 (7.9%)	76
14	75 (100.0%)	75	75 (98.7%)	76
28	75 (100.0%)	75	76 (100.0%)	76
35	74 (100.0%)	74	74 (100.0%)	74
42	73 (100.0%)	73	76 (100.0%)	76
84	72 (100.0%)	72	75 (100.0%)	75
112	70 (95.9%)	73	75 (98.7%)	76

Non-Inferiority test for ratio of two proportions is used for determining the sample size. The null hypothesis is that the ratio for the two treatments is less than the defined margin which is expressed as:

$$H_0: \emptyset \leq \emptyset_L \text{ where } \emptyset_L < 1$$

The sample size is estimated for an 80% power of demonstrating noninferiority of a 20% margin of non-inferiority and equal allowance (number of subjects in group 1 = number of subjects in group 2) with a p value = 0.025 (Table 7.8.3-2).

7.8.3-2 Noninferiority Sample Size and Percentage of Subjects with RVNA ≥ 0.05 IU/mL

Assumed SYN023 Proportion	Assumed HRIG Proportion	Margin	Total Sample Size
1	1	0.2	32
1	1	0.1	72

Samples sizes are shown for noninferiority for two proportions using a 20% margin that requires a total of 32 and a 10% margin that requires a total sample of 72 both of which can be demonstrated with the current 368 subject sample.

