7.8.4 Superiority of Secondary endpoint AUEC1-15

$H_0: \emptyset \leq \emptyset_L$ where $\emptyset_L > 1$

Where, $\emptyset = \frac{GM_{SYN023}}{GM_{HRIG}}$; GM is the geometric mean.

The alternative hypothesis for superiority is expressed as: $H_1: \emptyset > \emptyset_L$.

The calculation of the sample size requires defining the range of the true mean ratio [AUEC₁₋₁₅ (SYN023/RIG): 147.55%, 90% CI: 115.10%, 189.14%], margin of superiority [10%], power [80%], coefficient of variation [CV: 108.78%] and alpha [0.025]. The calculation is done in PASS 15 software for the defined range of the true mean ratio and the results are presented for only those values for which the sample size is considered feasible.

A true AUEC₁₋₅ geometric mean ratio of SYN023/ HRIG of at least 1.45 and 80% power would therefore require a sample size of 320 with equal number of subjects in two groups for detecting the superiority with 10% of margin. Based on a true geometric mean ratio of at least 1.45, a total sample size of 320. A higher total sample of 368 allows for drop-outs and lost to follow up.

7.8.5 Absence of Rabies:

Synermore estimates that any PEP failure rabies cases occurring in the trial will be more likely due to a failure of clinical management or failure to follow protocol specified procedures or less likely intrinsic resistance to post-exposure prophylaxis. Synermore estimates this possibility of rabies at approximately 0.1% to 0.01%. This means there is a small chance of a single case of confirmed rabies occurs in the 184 subjects in the SYN023 NRG group. If one case of PEP failure occurs the point incidence of PEP failure will be 0.6% and the 95% confidence interval will extend from 0% to 2.0%. A 0.6% failure rate is high enough to be evidence of lack of efficacy and thus a failure of the primary objective.

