3.1.6. Enrollment of the NRG

The NRG will consist of all WHO Category 3 exposure (Table 3.1-1). The NRG includes all rabies risks. It is powered to evaluate the primary and some secondary study objectives and to contribute to the pharmacokinetic and pharmacokinetic description of SYN023.

Subjects will be allocated with a 1:1 randomization to either SYN023 or HRIG treatment arms. Within the NRG group, bites to the head, neck or genitalia that have the highest rabies risk will be stratified for each treatment arm in a 1:1 ratio. The DSMB will review the progress of pharmacodynamic and safety data during the NRG study period to avoid unnecessary risk or expense.

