4.1. Sample Size

Data from the initial 20 LRG subjects will be evaluated by the DSMB to ensure pharmacodynamic activity before the remainder of the LRG is enrolled. The size of this group was determined by non-statistical reasons.

Safety and pharmacodynamic data from the entire LRG will be reviewed by the DSMB to ensure safety and pharmacodynamic adequacy. The size of the LRG is 80 subjects. Up to 45 LRG subjects will have received SYN023. This number was judged adequate to give a preliminary assessment of study drug performance in the LRG.

Three hundred and twenty patients are required in the Per-protocol Population to satisfy the efficacy elements of the AUEC₁₋₁₅ secondary endpoint. Synermore anticipates a total size of 368 subjects to be enrolled to NRG to allow a reasonable rate of loss to follow-up and exclusions. Since PEP should not be delayed and some inclusion/exclusion criteria may not be known at the time of randomization some subjects may be excluded (but not replaced) from the Per-protocol Population by the Per-Protocol Adjudication Board if they are later discovered to have met an exclusion criterion.

Detailed sample size considerations can be found in protocol Section 7.8 for full iterations.

Randomization will be adjusted by the randomization center such that patients are proportionately distributed between the trial sites and patients with wounds of the head, neck or genitalia are stratified approximately equally into the treatment groups.

Table 4.1-1 Sample Sizes by Risk Group and Treatment

Group	Enrollment	Treatment	Protocol version	Rabies Vaccination	Number of subjects
LRG	initial	HRIG 20 IU/kg	2.0	Study Days 1, 4, 8, 15	5
LRG	initial	SYN023 0.3 mg/kg	2.0	Study Days 1, 4, 8, 15	15
LRG	general	HRIG 20 IU/kg	3.0	Study Days 1, 4, 8, 15, 29	30

Group	Enrollment	Treatment	Protocol version	Rabies Vaccination	Number of subjects
LRG	general	SYN023 0.3 mg/kg	3.0	Study Days 1, 4, 8, 15, 29	30
NRG	general	HRIG 20 IU/kg	3.0	Study Days 1, 4, 8, 15, 29	184
NRG	general	SYN023 0.3 mg/kg	3.0	Study Days 1, 4, 8, 15, 29	184
Total required for initial LRG enrollment					20
Total required for general LRG enrollment					60
Total required for NRG enrollment					368
Total maximum enrollment					448

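### The Day 99 GMC non-inferiority sample size of 138 treats the standard error of the historical ratio as the between-subject CV; at the planning ratio of 0.88 the element has about 13% power, not 80%

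*Protocol*

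**What the plan says.** The primary objective joins four elements by AND (protocol 2.1, SAP 2.1). The second is non-inferiority of the Day 99 geometric mean RVNA concentration. SAP 8.1.1.2 declares success if the lower one-sided 97.5% bound for the SYN023/HRIG ratio exceeds 0.8.

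Protocol 7.8.2 sizes this element: "The sample size is calculated at 80% power with 20% margin of non-inferiority", with "number of subjects in group 1 = number of subjects in group 2) and alpha is taken to be 0.025". It concludes that the comparison "would require the sample size of 138 for 80% power with an expected true geometric means ratio 88.00"%. In Table 7.8-1 the row "Non inferiority Study Day 99 GMC" shows total N 138, ratio 0.88, margin 20% and CV 17.00%.

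The section takes its inputs from Table 7.8.2-2, "Ratio (SYN023/HRIG) and 95% Geometric Confidence Intervals for Each Time-point for RVNA from SYN023-002 Protocol, Historical Data". That table has a CV column of 13.59%, 13.04%, 16.47% and 17.32% for Days 35, 42, 84 and 112. By contrast, Section 7.8.4 sizes the AUEC endpoint with "coefficient of variation [CV: 108.78"%].

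SAP 3.1.6 says of the NRG: "It is powered to evaluate the primary and some secondary study objectives". Protocol 2.2.6 makes the same claim. SAP 4.1 adds no calculation of its own: "Detailed sample size considerations can be found in protocol Section 7.8 for full iterations".

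**The concern.** A between-subject CV of 17% cannot be squared with the historical data printed beside it. At Day 84 the earlier study had 72 + 75 = 147 subjects, an estimated ratio of 0.885 and a lower 95% limit of 0.64. The plan says that 138 subjects with a true ratio of 0.88 have an 80% chance of putting that limit above 0.80. With similar variability, both cannot hold.

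If the 17% is really the precision of an estimated ratio from about 150 subjects, the sample-size routine was given a spread that had already been divided by the square root of the sample size. Required numbers would then be understated many times over. Because the elements are joined by AND, a badly underpowered second element makes failure of the whole primary objective likely even when the assumed ratio of 0.88 is correct. The sponsor, DSMB and ethics committees would be relying on a power statement that does not hold.

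**Working it through.** **Method.** Work on the log scale with d = ln(true ratio / 0.80), σ = √ln(1 + CV²), two equal arms and one-sided alpha 0.025. The normal approximation is N = 4(1.960 + 0.842)²σ²/d² = 31.4σ²/d², rounded up to whole subjects per arm. Exact N and power use the noncentral t.

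**1. The plan's own figure.** Ratio 0.88 gives d = ln(1.10) = 0.0953. CV 17.00% gives σ² = ln(1.0289) = 0.0285. Then N = 31.4 × 0.0285 / 0.00908 ≈ 98.5, which is 100 after rounding up per arm and 102 by the noncentral t. The stated 138 is not reproduced. The Day 84 row (0.885, 16.47%) gives 86. The Day 112 row (0.8694, 17.32%) gives exactly 138, but so does ratio 0.88 with CV 20%.

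**2. What the CV column is.** From each printed 95% CI, SE of the log ratio = ln(upper/lower) / (2t), and its CV form is √(exp(SE²) − 1). Group sizes come from Tables 7.8.2-1 and 7.8.3-1.

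| Day | 95% CI of ratio | n per arm | SE | CV form of SE | Printed CV |
|---|---|---|---|---|---|
| 35 | 0.6219–1.0623 | 74, 74 | 0.1355 | 13.61% | 13.59% |
| 42 | 0.6879–1.1499 | 73, 76 | 0.1300 | 13.05% | 13.04% |
| 84 | 0.6404–1.2230 | 72, 75 | 0.1637 | 16.48% | 16.47% |
| 112 | 0.6188–1.2215 | 73, 76 | 0.1721 | 17.33% | 17.32% |

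All four agree to within 0.02 percentage points.

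**3. The between-subject spread, by two routes.**

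- From the ratio CIs, SD = SE / √(1/n₁ + 1/n₂). Day 84: 0.1637 / √(1/72 + 1/75) = 0.99. Day 112: 0.1721 / √(1/73 + 1/76) = 1.05. As CVs these are about 129% and 142%.
- From the single-arm CIs in Table 7.8.2-1, SD = √n × ln(upper/lower) / (2t). Day 84: SYN023 (1.79–3.03, n = 72) 1.12 and HRIG (2.27–3.33, n = 75) 0.83, pooled 0.98. Day 112: 1.16 and 0.93, pooled 1.05. As CVs the pooled values are about 128% and 141%.

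As a reverse check, a between-subject CV of 17% would give a Day 84 ratio CI of about 0.84–0.94; the protocol prints 0.64–1.22.

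**4. Check of the method on the AUEC row.** Ratio 1.45, margin 1.10 and CV 108.78% give σ = 0.884 and N = 322 (normal) or 324 (t), with 79.6% power at 320. The stated N is 320. That row therefore behaves as a between-subject calculation, and Table 7.8-1 holds two different quantities in one CV column.

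**5. Power with log SD 1.0.**

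| Subjects | True ratio 0.88 | True ratio 1.0 |
|---|---|---|
| 138 total (69 per arm) | 8% | 26% |
| 160 per arm (planned per-protocol) | 13.3% | 51% |
| 184 per arm (all NRG) | 14.7% | 57% |

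At 160 per arm and ratio 0.88, the pooled SDs of 0.98 to 1.05 give 13.7% to 12.5%. The separate arm SDs of 0.83 and 1.12 from Day 84 give 17.5% and 11.5%. N for 80% power at 0.88 is 31.4 × 1.0 / 0.00908 ≈ 3,460; the pooled SDs give about 3,350 to 3,790.

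**6. What a pass would need.** At 160 per arm the observed ratio must reach at least 0.80 × exp(1.967 × √(2/160)) = 0.997, so SYN023 would have to show virtually the same GMC as HRIG.

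**The case against.** The strongest reply is that the 13% is conditional. It holds at a true ratio of 0.88, a log SD of about 1.0 and 160 per arm. At a true ratio of 1.0 power is about 51%, so 13% is not a ceiling over every possible truth. That stands, and the conditions belong with the figure. It does not rescue the plan: 0.88 is the protocol's own planning ratio, and even equality leaves power far below 80%. Nor is it right that the element fails under every planning assumption, since the 17% CV is itself a listed assumption; were it true, power would be ample. The sound statement takes the assumed ratio together with the historical variability.

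Three further points stand as limits:

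- The origin of 138 in the Day 112 row is an inference, because another input pair gives the same number and no software output is shown.
- A CV of the ratio is a quantity the sponsor reports (SAP 8.1.1.1), so the column in Table 7.8.2-2 may be correct for what it is. The error lies in using it as a sample-size input.
- The back-calculation of the AUEC SD from its 90% CI, assuming 75 and 76 per arm, gives 0.92 rather than the 0.884 implied by 108.78%. The order of magnitude agrees, but not the exact value.

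The historical tables also disagree on the ratio. Table 7.8.2-1 gives 2.33/2.75 = 0.847 at Day 84, against 0.885 in Table 7.8.2-2. At 0.847, power at 160 per arm would be about 7%. The two tables may come from different analyses; the documents do not say.

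**Conclusion.** The concern holds. The 17.00% behind the sample size of 138 is on the scale of the standard error of a historical ratio, not of the spread between subjects, which the same section's intervals put at a CV of about 128% to 142%. At the planning ratio of 0.88 and 160 per arm, element 2 has about 13% power, and the composite can have no more than that. Separately, 138 does not follow from its labelled inputs, which give 102.

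The result assumes that the Day 84 and Day 112 variability of SYN023-002 carries over to Day 99 in this trial, which is the protocol's own planning basis, and that the printed intervals are t-based. Modest departures would not change the conclusion: 80% power at 0.88 with 160 per arm needs a log SD of about 0.30, less than a third of the historical value. Enrolment of 368 is driven by the AUEC endpoint, so correcting this row does not by itself change the NRG size.

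**What to change.** - In Table 7.8-1 and Section 7.8.2, replace the CV of 17.00% with the between-subject CV (about 130%, log SD about 1.0) and remove 138 as the number giving 80% power.
- Relabel the CV column of Table 7.8.2-2 as the CV of the estimated ratio. Check the Day 8 and Day 3 rows of Table 7.8-1 (16.11% and 9.83%) for the same substitution.
- State the power of element 2 at the planned per-protocol size (about 13% at ratio 0.88, about 51% at 1.0) and the resulting limit on composite power.
- Reconcile the ratios in Tables 7.8.2-1 and 7.8.2-2, and the Day 84 label on a Day 99 calculation.
- Correct the claim that the NRG is powered for the primary objective in protocol 2.2.6 and the study abstract, and in SAP 3.1.6. SAP 4.1 should point to the corrected section.

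The sponsor should then decide before unblinding, with regulatory agreement, whether the GMC comparison stays a pass/fail element. Protocol 7.3 and SAP 8.1.1.3 already rank the percentage at or above 0.5 IU/mL as the more important measure of vaccine compatibility, but changing a primary element is a design choice that the arithmetic does not settle.

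Restating the power costs only text and table edits and a much less favourable stated power. Actually powering this element at ratio 0.88 would take about 3,460 per-protocol subjects or a redesign.

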The alternative hypothesis (H_a) is that the SYN023 vaccine is non-inferior to HRIG by a 20% margin.

$$H_a: \emptyset = \frac{GMC_{SYN023}}{GMC_{HRIG}} > 0.8$$

The null hypothesis is:

$$H_0: \emptyset = \frac{GMC_{SYN023}}{GMC_{HRIG}} \leq 0.8$$

The null hypothesis will be rejected at a significance level of 2.5% ($\alpha = 0.025$) if the lower bound of the one-sided 97.5% confidence interval for the GMC ratio is greater than the non-inferiority bound 0.8. Descriptive statistics will be displayed in a summary table following the same presentation for Section 8.1.1.1.

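### The Day 99 GMC non-inferiority total of 138 does not follow from the inputs printed beside it (ratio 0.88, CV 17.00%, 80% power), which give 102; the source of 138 is unclear and neither figure is safe on the printed CV

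*Protocol*

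**What the plan says.** Protocol Section 7.8.2 sizes the second primary element, non-inferiority of the Study Day 99 RVNA geometric mean concentration. The stated settings are:

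- Power, margin and allocation: "The sample size is calculated at 80% power with 20% margin of non-inferiority and equal allowance" between the arms.
- Bound: the 20% margin was chosen because "it is a recommended bioequivalence margin for a lower bound of 0.8".
- Alpha: "alpha is taken to be 0.025". SAP Section 8.1.1.2 makes the test one-sided, rejecting if the "lower bound of the one-sided 97.5% confidence interval for the GMC ratio is greater than the non-inferiority bound 0.8".
- Result: "would require the sample size of 138 for 80% power with an expected true geometric means ratio 88.00" percent. The subject of that sentence is "The non-inferiority of serum GMC RVNA on study day 84 in SYN023 recipients", although the endpoint is Day 99.

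The Table 7.8-1 row "Non inferiority Study Day 99 GMC" repeats total 138, ratio 0.88 and margin 20%, and adds a CV of 17.00%. Table 7.8.2-2, described as the source of the software inputs, has no row with 0.88 or 17.00%. Its nearest rows are Day 84 (88.50%, CV 16.47%) and Day 112 (86.94%, CV 17.32%). SAP Section 4.1 refers back to Protocol Section 7.8 and does not repeat the calculation.

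**The concern.** Every input to this calculation is printed, so a reader should be able to recover 138, and cannot. The sentence, the summary table and the source table point to three different days (84, 99 and 112).

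The element is one of four that must all be met for the primary objective to succeed, so its power statement should be traceable. The required size is also very sensitive to these inputs: going from 0.88 / 17.00% to 0.8694 / 17.32% moves the total from 102 to 138. Anyone who re-powers the element needs to know which ratio and which CV were intended.

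**Working it through.** **Method.** Two-sample comparison of log concentrations with equal arms. σ² = ln(1 + CV²) and δ = ln(ratio / 0.80). The normal approximation is n per arm = 2σ²(1.960 + 0.842)² / δ² = 2σ² × 7.849 / δ². Exact figures use the noncentral t distribution.

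**Check of method.** The AUEC1-15 inputs in Section 7.8.4 (ratio 1.45, bound 1.10, CV 108.78%, alpha 0.025) give 322 by normal approximation and 324 by noncentral t, with 79.6% power at the stated 320. The method recovers the protocol's other geometric-mean calculation to within 2 to 4 subjects.

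**Printed inputs (0.88, 17.00%).** σ² = ln(1.0289) = 0.02849; δ = ln(1.10) = 0.09531; δ² = 0.009084. n = 2 × 0.02849 × 7.849 / 0.009084 = 49.2, so 50 per arm and 100 in total. Noncentral t gives 51 per arm, **102 in total**. Power at 69 per arm (138) is **90.9%**.

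**Rows of Table 7.8.2-2, same method (noncentral t).**

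| Row | Ratio | CV | Total N for 80% power |
|---|---|---|---|
| Day 35 | 81.28% | 13.59% | 2,284 |
| Day 42 | 88.94% | 13.04% | 50 |
| Day 84 | 88.50% | 16.47% | 86 |
| Day 112 | 86.94% | 17.32% | 138 |

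For Day 112: σ² = 0.02956; δ = ln(0.8694 / 0.80) = 0.08319; n = 2 × 0.02956 × 7.849 / 0.006920, about 67, so 68 per arm (136) by normal approximation and 69 per arm (138) by noncentral t, with 80.6% power.

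**Is Day 112 the only route to 138?** No. Ratio 0.88 with CV 20%, and ratio 0.87 with CV 17.5%, each give 138 by noncentral t. Ratio 0.88 with CV 17.32% at 90% power gives 138 by normal approximation.

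**Variants at the printed ratio and CV.** None gives 138:

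- 90% power: 134 (132 by normal approximation)
- one-sided alpha 0.0125: 122
- one-sided alpha 0.05: 80
- ratio of arithmetic means (Fieller): 118
- 102 inflated for 15% dropout: 102 / 0.85 = 120

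**What the CV column is.** From the 95% intervals in Table 7.8.2-2 and the arm sizes in Table 7.8.2-1:

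- Day 84: SE of log ratio = ln(1.2230 / 0.6404) / (2 × 1.976) = 0.164. As a CV, √(exp(0.164²) − 1) is about 16.5%, against 16.47% printed.
- Day 112: ln(1.2215 / 0.6188) / (2 × 1.976) = 0.172, or about 17.3%, against 17.32% printed.

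These are standard errors of the historical ratio, not between-subject spread. The between-subject log SD is SE / √(1/n₁ + 1/n₂): 0.164 / √(1/72 + 1/75), about 0.99, and 0.172 / √(1/73 + 1/76), about 1.05 (CVs of about 129% and 142%). At ratio 0.88 and bound 0.80, these need about 3,400 and 3,800 subjects in total for 80% power. At 320 per-protocol subjects, power is 13.5% and 12.5%.

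**The case against.** The best defence is that nothing in the design rests on 138. The 320 per-protocol subjects, and the 368 enrolled, come from AUEC1-15. On the sponsor's own CVs, power at 320 is about 99.9% at 0.88 / 17.00% and 99.1% at 0.8694 / 17.32%. The discrepancy is also conservative on its face, since 138 exceeds 102. All of that stands, and it limits the point to the traceability of a power statement.

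It can also be said that the Day 112 match is weak evidence of origin. The method misses the AUEC1-15 row by 2 to 4 subjects, other input pairs also return 138, and Section 7.8.2 argues expressly for 0.88 on the ground that the ratio is stable from Day 42 to Day 112. That too stands. A reader might infer that the sponsor sized the element on Day 112 data and mislabelled it, but the documents do not include the software output and do not support that as a finding. The wrong item could be the ratio, the CV, the N or the power.

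None of this closes the gap between 102 and 138, which is far beyond rounding or choice of approximation.

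**Conclusion.** The stated total and power do not follow from the stated inputs: 102 against 138 in total (138 is 35% higher), or 90.9% against 80% power. The Day 84 label does not fit either, because that row gives 86. This rests on the log-normal two-sample test that the protocol names, with the bound, alpha and allocation it states. The source of 138 remains open, with Day 112 a plausible candidate only.

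A reader might also infer that the element is comfortably powered and that 102, or 91% at 138, is the corrected figure. The documents do not support that. The CVs in Table 7.8.2-2 behave as standard errors of the historical ratio, and the 17.00% in Table 7.8-1 is of the same size. On the spread implied by the protocol's own intervals, power at 320 is about 12-14% at ratio 0.88. That range assumes the Day 84 and Day 112 spread carries over to Day 99 in this trial.

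**What to change.** 1. Retrieve the PASS 15 output for this element. Correct whichever of ratio, CV, N or power is wrong, so that Table 7.8-1 and Section 7.8.2 agree.
2. Replace the Study Day 84 reference with the timepoint actually used, and say how it supports Day 99.
3. Do not print 102, or 91% power at 138, on the current CV. Recompute the element with a between-subject CV (log SD about 0.99 to 1.05 from the same intervals) and the declared ratio, and restate the power at 320 per-protocol subjects.

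The cost is one software re-run and a wording change in Section 7.8. No change to enrolment is proposed.
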